5.0 Subject Disposition

The total number of subjects who were treated will be summarized.

The number of subjects for each of the following categories will be summarized by treatment group randomized in M16-046 in the ITT Population:

- Subjects who completed protocol-specified treatment;
- Subjects who prematurely discontinued study drug (all reasons and primary reason);
- Subjects who completed the study;

Number and percentage of subjects who discontinued study drug will be summarized by reason (primary reason and all reasons). Subjects with multiple reasons for premature discontinuation will be counted once in the calculation of the number and percentage of total discontinuations.

6.0 Study Drug Duration and Compliance

Study Drug Duration (in Days):

Summary of study drug duration and study drug compliance will be provided in M19-850 for the Safety Population during the entire treatment period. Study drug duration (days) will be summarized using the number of subjects, mean, standard deviation, minimum, median and maximum for each treatment group.

• Duration of upadacitinib is defined for each subject as last dose date of upadacitinib minus first dose date of upadacitinib +1,

[figure not shown]
In addition, the number and percentage of subjects exposed to upadacitinib will be summarized for the following categories of exposure duration for the Safety Population starting from the first dose of upadacitinib in M16-046 or M19-850:

- \bullet > 4 weeks
- ≥ 12 weeks
- \geq 24 weeks
- \geq 36 weeks
- \geq 48 weeks
- \geq 52 weeks
- \geq 64 weeks
- ≥ 76 weeks
- \geq 88 weeks
- ≥ 100 weeks
- ≥ 112 weeks
- \geq 124 weeks
- ≥ 136 weeks
- ≥ 148 weeks
- ≥ 160 weeks

Compliance:

Treatment compliance will be summarized in the Safety Population for the entire treatment period.

Upadacitinib compliance for an individual subject is defined as the number of upadacitinib actually taken (i.e., the difference between the number of tablets dispensed and the number of tablets returned) by the subject divided by the number of tablets planned to be taken by the subject during the study.

7.0 Demographics, Baseline Characteristics, Medical History, and Prior/Concomitant Medications

Demographics, baseline or disease characteristics, and medical history will be summarized for ITT overall and by M16-046 treatment group. Categorical variables will be summarized with the number and percentage of subjects; percentages will be calculated based on the number of non-missing observations. Continuous variables will be summarized with descriptive statistics (number of non-missing observations, mean and standard deviation, median, minimum and maximum). Prior and concomitant medications will be summarized for the Safety Population overall and by M16-046 treatment group.

7.1 Demographics and Baseline Characteristics

Subject Demographics

The following demographic and Baseline parameters will be summarized.

Unless otherwise specified, the baseline below refers to the baseline of Study M16-046.

Subject Demographics

- Sex (male, female)
- Age (years), defined as the number of years from date of birth to date of first drug
- Age categories ($< 40, \ge 40 \text{ to } < 65, \ge 65 \text{ years}$).
- Race (White, Black or African American, Asian, American Indian or Alaska Native, Native Hawaiian or Other Pacific Islander, Other, Multi Race)
- Ethnicity (Hispanic or Latino, Not Hispanic or Latino)
- Body weight (kg)

General Baseline Characteristics at the Entry of Study M16-046 and Study M19-850

- EASI (Eczema Area and Severity Index)
- BSA (Body Surface Area) with Atopic Dermatitis

- Worst Pruritus NRS
- Daily Worst Pruritus NRS (Entry of Study M16-046 only)
- IGA categories (< 3 or missing, 3, 4) (Entry of Study M16-046 only)

Atopic Dermatitis History

- Duration of Atopic Dermatitis since diagnosis (years)
- Duration of Atopic Dermatitis between symptoms and diagnosis (years)

Nicotine and Alcohol Use

- Smoking history (Unknown, Never, Current, Former)
- Alcohol History (Unknown, Never, Current, Former)

[figure not shown]
7.2 Medical History

Medical history data will be coded using the Medical Dictionary for Regulatory Activities (MedDRA). The actual version of the MedDRA coding dictionary will be noted in the statistical tables and clinical study report. The number and percentage of subjects in each medical history category (by MedDRA system organ class and preferred term) will be summarized. The system organ class (SOC) will be presented in alphabetical order, and the preferred terms will be presented in alphabetical order within each SOC. Subjects reporting more than one condition/diagnosis will be counted only once in each row (SOC or preferred term).

Medical history will be summarized in the ITT Population.

7.3 Prior and Concomitant Medications

Prior and concomitant medications will be summarized by generic name. A prior medication is defined as any medication taken prior to the date of the first dose of study drug of Study M16-046. A concomitant medication is defined as any medication that started prior to the date of the first dose of study drug of Study M19-850 and continued to

be taken after the first dose of study drug of Study M19-850 or any medication that started on or after the date of the first dose of study drug of Study M19-850, but not after the date of the last dose of study drug of Study M19-850. The number and percentage of subjects taking medications will be summarized by generic drug name based on the World Health Organization (WHO) Drug Dictionary for both prior and concomitant medications.

Prior and concomitant medications will be summarized in the Safety Population.

8.0 Handling of Potential Intercurrent Events for the Primary and Key Secondary Endpoints

Since M19-850 does not have primary or secondary efficacy endpoints, so there is no handling of potential intercurrent events for them.

9.0 Efficacy Analyses

9.1 General Considerations

[figure not shown]
An Interim Analysis will be performed after all ongoing subjects have completed the Week 16 visit. The Final database lock will be performed at the end of study.

Efficacy variables will be summarized in the Study M19-850 ITT Population at each visit of Study M16-046 and Study M19-850, unless otherwise specified. No statistical testing will be performed.

A subject's M16-046 Baseline is defined as the last non-missing observation on or before their first dose of study drug in M16-046. For randomized but not treated subjects, the Baseline value will be the last non-missing measurement recorded prior to randomization. All efficacy endpoints defined below are relative to the M16-046 Baseline unless otherwise specified.

Efficacy assessments for ITT Population will be presented for the following three groups at each visit:

• subjects originally randomized to dupilumab in Study M16-046

- subjects originally randomized to upadacitinib in Study M16-046
- ITT Population (only applicable at visits of Study M19-850)

Continuous variables will be summarized by the number of observations, mean, standard deviation, median, minimum, maximum, 25th and 75th percentiles, as well as the 95% confidence intervals (CIs) of the mean values. Categorical variables will be summarized by counts and percentages, as well as the 95% CIs of the percentages.

The Observed Cases (OC) approach as defined in Section 9.2 will be used for all efficacy variables.

Analysis of Categorical Variables

For ITT Population, frequencies and percentages will be summarized along with 95% confidence interval (CI) based on normal approximation.

OC will be the only approach for categorical endpoints (Section 9.2).

Analysis of Continuous Variables

For ITT Population, the raw values at each visit and Baseline, change from Baseline/percent change from Baseline will be presented for the three treatment groups mentioned in this Section who have both Baseline and post-baseline visit values. The mean, 95% confidence interval, standard error, Min, Q1, median, Q3 and Max will be summarized.

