7.3 Statistical Analyses for Efficacy

All efficacy endpoints will be summarized in the ITT population.

The ITT Population will be summarized by treatment group as randomized at the Baseline of Study M16-046.

Continuous variables will be summarized by the number of observations, mean, standard deviation, median, minimum, maximum, as well as the 95% confidence intervals (CIs) of the mean values. Categorical variables will be summarized by counts and percentages, as well as the 95% CIs of the percentages.

There will be no statistical testing for all of the efficacy and safety endpoints.

Efficacy assessments will be summarized by Observed Cases (OC) approach. No data imputation will be applied. Observed Cases will not include values after a subject prematurely discontinue from study drug.

Sample Size Estimation

Approximately 600 subjects that complete treatment in Study M16-046 will roll over in this open label treatment extension study. The sample size is determined by the completion of Study M16-046 and the consenting for the extension.

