2.4 Sample Size Determination

Approximately 600 subjects who complete treatment in Study M16-046 will roll over in this open label treatment extension study. The sample size is determined by the expected rate of completion of Study M16-046 and subject consent for the extension.

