3.3 Other Efficacy Endpoints

The following efficacy endpoints will be assessed at all visits through Week 52. Baseline refers to the Baseline value in Study M16-046. All endpoints are defined relative to the Baseline values in Study M16-046.

- Change and percent Change from Baseline in EASI;
- Change and percent change from Baseline in Worst Pruritus Numerical Rating Scale (NRS);
- Proportion of subjects achieving EASI 75/90/100;
- Change from Baseline in body surface area (BSA);
- Proportion of subjects achieving an improvement (reduction) in Worst Pruritus NRS ≥ 4 from Baseline among subjects who had Worst Pruritus NRS ≥ 4 at Baseline;
- Proportion of subjects achieving 75% reduction in EASI in the head and neck body region from Baseline;

- Proportion of subjects achieving 75% reduction in EASI in each body region (other than head and neck) from Baseline;
- Proportion of subjects achieving 75% reduction in EASI in the head and neck body region among subjects who received dupilumab in Study M16-046 and did not achieve 75% reduction in EASI in the head and neck body region at Week 24 of Study M16-046;
- Proportion of subjects achieving 75%/90%/100% reduction in EASI (EASI 75/90/100) among subjects who received dupilumab in Study M16-046 and did not achieve EASI 75 at Week 24 of Study M16-046;
- Proportion of subjects achieving EASI 90/100 among subjects who received dupilumab in Study M16-046 and did not achieve EASI 90 at Week 24 of Study M16-046;
- Proportion of subjects achieving EASI 100 among subjects who received dupilumab in Study M16-046 and did not achieve EASI 100 at Week 24 of Study M16-046;
- Proportion of subjects achieving an improvement (reduction) in Worst Pruritus NRS reduction ≥ 4 among subjects who had Worst Pruritus NRS ≥ 4 at Baseline, received dupilumab in Study M16-046 and did not achieve Worst Pruritus NRS reduction ≥ 4 at Week 24 of Study M16-046.

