9.2 Handling of Missing Data

Missing data will be handled using the following methods for the efficacy analyses:

• Observed Cases (OC): The OC analysis will not impute values for missing evaluations, and thus a subject who does not have an evaluation on a scheduled visit will be excluded from the OC analysis for that visit. OC will exclude values after a subject prematurely discontinue from study drug + 1 days.

OC will be the only imputation method for all the efficacy endpoints.

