9.5 Additional Efficacy Analyses

Other efficacy endpoints are listed in Section 3.3. The analysis detail is specified in Section 9.1.

[figure not shown]
The following endpoints will be summarized only at the visits of Study M18-850.

- Proportion of subjects achieving 75% reduction in EASI in the head and neck body region among subjects who received dupilumab in Study M16-046 and did not achieve 75% reduction in EASI in the head and neck body region at Week 24 of Study M16-046;
- Proportion of subjects achieving 75%/90%/100% reduction in EASI (EASI 75/90/100) among subjects who received dupilumab in Study M16-046 and did not achieve EASI 75 at Week 24 of Study M16-046;
- Proportion of subjects achieving EASI 90/100 among subjects who received dupilumab in Study M16-046 and did not achieve EASI 90 at Week 24 of Study M16-046;
- Proportion of subjects achieving EASI 100 among subjects who received dupilumab in Study M16-046 and did not achieve EASI 100 at Week 24 of Study M16-046;
- Proportion of subjects achieving an improvement (reduction) in Worst Pruritus NRS reduction ≥ 4 among subjects who had Worst Pruritus NRS ≥ 4 at Baseline, received dupilumab in Study M16-046 and did not achieve Worst Pruritus NRS reduction ≥ 4 at Week 24 of Study M16-046.

Missing data will be imputed as specified in Section 9.2.

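### SAP 9.1 gives every response proportion a normal-approximation 95% CI, which fails when the rate is near 0% or 100%, and most in small non-responder subsets

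*SAP*

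**What the plan says.** The protocol (7.3, Statistical Analyses for Efficacy) asks for intervals but names no method: "Categorical variables will be summarized by counts and percentages, as well as the 95% CIs of the percentages". The SAP makes the choice. In 9.1, under the analysis of categorical variables, "frequencies and percentages will be summarized along with 95% confidence interval (CI) based on normal approximation".

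SAP 9.5 carries that choice to every endpoint listed in SAP 3.3: "The analysis detail is specified in Section 9.1". These include five endpoints restricted to dupilumab non-responders, for example EASI 75/90/100 "among subjects who received dupilumab in Study M16-046 and did not achieve EASI 75 at Week 24 of Study M16-046".

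Neither section gives a formula, a rule for small denominators, or a rule for an observed 0% or 100%. Three other statements bear on the point:

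- Size (SAP 2.4): "Approximately 600 subjects who complete treatment in Study M16-046 will roll over in this open label treatment extension study". This is a rollover count, not the result of a precision calculation.
- Denominators (SAP 9.2): under observed cases, "a subject who does not have an evaluation on a scheduled visit will be excluded from the OC analysis for that visit", so n can shrink at later visits.
- Role of the intervals (SAP 9.1): "No statistical testing will be performed".

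**The concern.** The textbook normal-approximation interval for a proportion takes its standard error from the observed rate. As that rate approaches 0% or 100%, the standard error shrinks towards zero and the interval becomes too short, whatever the real uncertainty.

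Some planned cells could lie in that region. EASI 100 among subjects who missed EASI 75 at Week 24 applies the strictest threshold to people selected for non-response. For the endpoints that keep the same threshold as the selection rule, every subject starts as a non-responder, so the earliest extension visits move up from zero. SAP 9.1 also tabulates the main efficacy variables at each visit of Study M16-046, where early EASI 90/100 rates may be low. At the other end, EASI 75 could approach its ceiling under continued treatment. None of these rates is stated in the documents; they are possibilities that follow from the design.

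With no testing planned, the interval is the only planned measure of precision for a proportion. Where the rate is extreme, a reader would see limits that are too narrow, impossible, or 0–0%, and would take the estimate as more certain than it is.

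**Working it through.** **Inputs.** From the documents: confidence level 95%, taken as two-sided (z = 1.96, z² = 3.84); about 600 subjects in total (SAP 2.4). Assumed, because the documents do not give them: subset sizes n = 30 to 300 (600 for the full ITT Population) and true rates p from 1% upwards. Results for p and 1−p are identical by symmetry. There is no power or precision figure in the plan to reproduce; the figure under test is the nominal 95%.

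**Formulas**, with p̂ = x/n:

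- Wald: p̂ ± z·√[p̂(1−p̂)/n]
- Wilson score: [p̂ + z²/(2n) ± z·√(p̂(1−p̂)/n + z²/(4n²))] / (1 + z²/n)
- Exact coverage: the sum of Binomial(n, p) probabilities over every x whose interval contains p

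**When Wald leaves 0–100%.** The lower limit is negative when p̂ < z·√[p̂(1−p̂)/n], that is, when x/(1 − x/n) < 3.84. At x = 4 this never holds. At x = 3 it holds once n ≥ 14. So, from n = 14 upwards, one to three responders give a negative lower limit and zero responders give zero width. The same applies to non-responders at the top end.

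**One cell worked through: n = 30, p = 5%.** The Wald interval contains 5% only for x = 1 to 5. It misses at x = 0 (probability 0.95³⁰ = 21.5%) and at x ≥ 6 (0.3%), so coverage is 100 − 21.5 − 0.3 = 78.2%. Outcomes x = 1, 2, 3, which give a negative lower limit, have probability 33.9 + 25.9 + 12.7 = 72.5%. Adding x = 0, about 94% of the time the interval would be zero-width or out of range.

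**Coverage at single points:**

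| n | true rate | Wald | Wilson | zero-width or out of range (Wald) |
|---|---|---|---|---|
| 30 | 5% | 78.2% | 93.9% | 94% |
| 80 | 2% | 80.0% | 97.8% | 92% |
| 150 | 2% | 80.0% | 96.8% | 65% |
| 300 | 1% | 79.9% | 96.7% | 65% |
| 300 | 2% | 93.2% | 94.2% | 15% |
| 300 | 5% | 92.6% | 95.5% | 0% |
| 600 | 2% | 94.5% | 94.5% | 0.2% |
| 30 | 20% | 94.6% | 96.4% | 12% |
| 300 | 50% | 94.3% | 94.3% | 0% |

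Binomial coverage oscillates with n and p, so single points can mislead. Averages are the fairer summary.

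**Average coverage, Wald / Wilson:**

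| n | rates 2–10% | rates 20–80% |
|---|---|---|
| 30 | 79.1 / 95.9 | 93.0 / 95.1 |
| 80 | 90.1 / 95.6 | 94.3 / 95.1 |
| 150 | 91.9 / 95.3 | 94.6 / 95.0 |
| 300 | 93.5 / 95.1 | 94.8 / 95.0 |
| 600 | 94.3 / 95.1 | 94.9 / 95.0 |

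**What a table would show:**

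| observed | Wald | Wilson |
|---|---|---|
| 0/40 | 0 to 0% | 0 to 8.8% |
| 1/40 | −2.3 to 7.3% | 0.4 to 12.9% |
| 48/50 | 90.6 to 101.4% | 86.5 to 98.9% |
| 30/60 | 37.3 to 62.7% | 37.7 to 62.3% |

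For 1/40: Wald is 2.5% ± 1.96 × √(0.025 × 0.975/40) = 2.5% ± 4.8%.

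**The case against.** The strongest reply is that no affected cell can be shown. The documents give no allocation for Study M16-046, no count of Week 24 non-responders and no expected response rates. The subsets defined by missing EASI 90 or EASI 100 contain everyone who missed EASI 75, so they are at least as large as that one. This stands: the finding is conditional.

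Second, the worst single cells are troughs. At n=150, moving the rate from 2% to 3% lifts Wald coverage from 80.0% to 93.6%; at n=300, moving from 1% to 2% lifts it from 79.9% to 93.2%. This also stands, and is why the averages matter. Averaged over 2–10% the loss is severe only for small subsets; at n=300 it is about 1.5 points.

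Third, the Wilson interval also rests on a normal approximation. If that is what the SAP means, the defect largely disappears and what remains is an unnamed formula. Wald is the likelier reading, and naming the method settles the matter either way.

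Fourth, the endpoints are exploratory and counts appear beside the intervals, so a reader can spot 0–0% or 101.4% and recompute. That limits the harm but does not justify printing such limits. Truncating at 0% and 100% would hide impossible values without restoring coverage or curing zero width.

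Finally, the interim analysis had a data cutoff of 09MAR2021 and this SAP is version 5.0 of 01 August 2023, so a change now could leave interim and final tables on different intervals. Re-running the proportion tables deals with that.

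**Conclusion.** The concern holds. Followed as written and read as Wald, SAP 9.1 gives zero-width, out-of-range or under-covering intervals wherever a response rate is close to 0% or 100%. The loss is large when the denominator is also small (average coverage 79.1% at n=30 for rates of 2–10%), moderate at n=80 to 150 (90.1% to 91.9%), and minor for the full population of about 600 (94.3%). Mid-range proportions are adequately served.

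The conclusion rests on the Wald reading and on assumed subset sizes and rates; how many reported cells would be affected cannot be determined from the documents. The consequence is confined to descriptive intervals on exploratory endpoints. No test or decision depends on them. It is a modest point, worth correcting because the correction is so cheap.

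**What to change.** In SAP 9.1, replace the reference to a normal approximation with a named method: the Wilson score 95% interval for all proportions. If the team prefers guaranteed coverage of at least 95%, name Clopper-Pearson instead, accepting that it is somewhat conservative (98.4% against Wilson's 93.9% at n=30 and 5%). Choose one and use it throughout. SAP 9.5 needs no edit because it points to 9.1, and protocol 7.3 needs none because it names no method.

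The cost is one phrase in the SAP and one option in the SAS program. No point estimate changes. Intervals at extreme rates become wider within the possible range, and mid-range ones hardly move. Any interim proportion tables that will be shown beside the final ones should be re-run with the same method, which needs no new data.

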9.2 Handling of Missing Data

Missing data will be handled using the following methods for the efficacy analyses:

• Observed Cases (OC): The OC analysis will not impute values for missing evaluations, and thus a subject who does not have an evaluation on a scheduled visit will be excluded from the OC analysis for that visit. OC will exclude values after a subject prematurely discontinue from study drug + 1 days.

OC will be the only imputation method for all the efficacy endpoints.

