5.4 Prior and Concomitant Therapy

Any medication or vaccine (including over-the-counter or prescription medicines, vitamins and/or herbal supplements) that the subject is receiving at the time of the Baseline visit and/or receives during the study, must be recorded along with the reason for use, date(s) of administration including start and end dates, and dosage information including dose, route and frequency on the appropriate electronic case report form (eCRF). Also, medications taken for AD since date of diagnosis (based on subject recollection and available medical records) should be reviewed.

If there are any questions regarding concomitant or prior therapies, the AbbVie TA MD should be contacted.

Required Concomitant Medications

Twice daily use of an additive-free, bland emollient that was used during Study M16-046 should be continued for the duration of Study M19-850.

Note: Subject may use prescription moisturizers or moisturizers containing ceramide, urea, filaggrin degradation products or hyaluronic acid if such moisturizers were initiated before Study M16-046 Baseline visit.

Rescue Therapy

Rescue treatment for AD may be provided, if medically necessary, at the discretion of the investigator.

Investigators should attempt to limit the first step of rescue therapy to topical medications and escalate to systemic medications only for those subjects who do not respond adequately after at least 7 days of topical treatment.

If a subject needs rescue treatment with a systemic agent (including but not limited to corticosteroids, cyclosporine, methotrexate, mycophenolate mofetil, azathioprine) or phototherapy, study drug should be permanently discontinued prior to the initiation of rescue systemic agent or phototherapy and subject should be discontinued from the study.

Investigators should conduct efficacy and safety assessments (e.g., disease severity scores, safety labs) before administering any rescue treatment. An unscheduled visit may be used for this purpose if necessary.

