		Appendix F: Added this section to include the activity schedule.

 Table 2.
 SAP Version History Summary (Continued)

Version	Date	Summary
3.0	14 April 2021	Section 10.2.7: Deleted 'listings of pre-treatment AE' as they are not needed for this open label extension study.
4.0	21 June 2021	Section 5.0: Clarified that subjects who were rescued in the study will not be summarized.
		Section 6.0: Clarified that study drug duration and compliance will be summarized based on Safety Population.
		Section 7.1: Modified the demographics section to be consistent with eCRF design.
		Section 7.1: Added the Worst Pruritus NRS summary for both M16-046 and M19-850 Baseline, as well as Daily NRS for M16-046 Baseline.
		Section 10.2.3: Clarified that the TEAE will be summarized by SOC and PT and maximum toxicity instead of by maximum toxicity and SOC and PT.

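### Values after topical rescue count as ordinary response and no planned table identifies rescue, so the reader cannot tell how much rescue contributed to the efficacy percentages

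*SAP*

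**What the plan says.** **Rescue rules.** Protocol 5.3 bars starting topical treatment for atopic dermatitis (AD) while on study drug, with rescue as the exception. Protocol 5.4 then states "Rescue treatment for AD may be provided, if medically necessary, at the discretion of the investigator". The order is topical first: "Investigators should attempt to limit the first step of rescue therapy to topical medications". No limit is given on the potency, duration or number of topical courses, and nothing requires study drug to stop for topical rescue. For systemic agents and phototherapy, "study drug should be permanently discontinued prior to the initiation of rescue systemic agent or phototherapy". On timing, Protocol 5.4 says "Investigators should conduct efficacy and safety assessments (e.g., disease severity scores, safety labs) before administering any rescue treatment" and adds "An unscheduled visit may be used for this purpose if necessary".

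**Analysis rules.** SAP 9.2 imputes nothing and omits a subject from any visit without an evaluation. Its only other exclusion is "OC will exclude values after a subject prematurely discontinue from study drug + 1 days". Protocol 7.3 names the same single trigger. SAP 9.1 and 9.2 make OC the only approach for every efficacy endpoint. SAP 8.0 concerns primary and key secondary efficacy endpoints, finds none, and concludes that "there is no handling of potential intercurrent events for them".

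**Reporting rules.** SAP 5.0 has no rescue category. The version 4.0 entry for that section in SAP 14.0 is consistent with this: "Clarified that subjects who were rescued in the study will not be summarized". SAP 7.0 and 7.3 summarise concomitant medications by generic name, overall and by M16-046 group, without indication or timing.

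**The concern.** New topical AD therapy is controlled in this study because it can change the skin and itch scores that the efficacy endpoints measure. Once given as rescue, however, it leaves no trace in the efficacy analysis. A subject who flares, starts a topical anti-inflammatory agent, stays on upadacitinib and meets EASI 75 at the next visit is a responder in the same sense as one who never needed rescue.

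On-drug rescue is foreseen. Protocol 5.5 works through a case in which rescue is given at the M19-850 Baseline and the subject is assessed at Weeks 4 and 8. That Baseline is also the day on which dupilumab subjects switch. A dupilumab non-responder could therefore start upadacitinib and topical rescue together and be reported as a switch responder at Week 4. No planned output would show that rescue had been used.

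The use of these results matters more than their formal rank. Efficacy is part of the study objective (Protocol 3.1). The stated rationale for the Week 16 interim analysis is to look at efficacy and safety after the switch from dupilumab (Protocol Appendix E). Five endpoints in SAP 9.5 are restricted to dupilumab subjects who missed a response threshold at Week 24. The two origin groups are also shown side by side, and rescue use could differ between them.

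**Working it through.** **No planned figure to reproduce.** The sample size of about 600 is a roll-over count with no effect size, alpha or power (SAP 2.4), and no efficacy testing is planned (SAP 9.1). The point rests on the text. The arithmetic only shows how much the handling of rescue could matter.

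**Step 1: what happens to each type of value.**

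| Situation | Study drug | In OC? | Identified as rescue in a table? |
|---|---|---|---|
| No rescue | continues | yes | not applicable |
| Topical rescue | continues | yes, as an ordinary value | no; the agent is listed by generic name only |
| Systemic rescue or phototherapy | must stop | no, once past the discontinuation cut-off | no; at most visible through discontinuation reasons |

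Only the middle row puts post-rescue values into the efficacy results.

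**Step 2: size.** For one binary endpoint at one visit, let
- r = share of observed subjects with topical rescue by that visit
- q = response rate among those rescued
- p = response rate among those not rescued

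The documents give none of these; all are assumptions.

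- Planned OC rate: (1 − r)p + rq
- Rate if rescue counts as non-response: (1 − r)p
- Difference: rq, which does not depend on p

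Example with r = 10%, p = 80%, q = 50%: OC = 0.90 × 0.80 + 0.10 × 0.50 = 77.0%. With rescue as non-response, 0.90 × 0.80 = 72.0%. The difference is 5.0 points, or 30 of 600 subjects.

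| r | q = 30% | q = 50% | q = 80% |
|---|---|---|---|
| 2% | 0.6 | 1.0 | 1.6 |
| 5% | 1.5 | 2.5 | 4.0 |
| 10% | 3.0 | 5.0 | 8.0 |
| 20% | 6.0 | 10.0 | 16.0 |

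(differences in percentage points)

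**Step 3: a yardstick.** SAP 9.1 uses normal-approximation 95% intervals. At an 80% rate the half-width is 1.96 × √(0.80 × 0.20 / 600) = 3.2 points for 600 subjects, and 4.5 points for an assumed origin group of 300. At r = 2% the choice of rule moves the rate by less than the interval half-width. At r = 5–10% and q = 50–80% it moves it by 2.5 to 8.0 points, which is comparable to or larger than the half-width for 600. Without a rescue table nobody can say which case applies.

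**The case against.** The strongest reply is that this is a single-arm, open-label extension with safety as the primary objective and exploratory, untested efficacy. Counting observed values regardless of topical rescue is a recognisable treatment-policy approach, and Protocol 7.3 had already set it. That stands: OC is a legitimate main analysis and should stay. It does not remove the need to say what the percentage describes.

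Several stronger readings are tempting, and the documents do not support them.

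- *Rescue is unlimited.* It must be medically necessary and should start with topical agents. Study drug stops for systemic rescue, for rescue outside Protocol 5.4, and for EASI worsening of 25% or more at two consecutive scheduled visits after a trial of rescue where appropriate (Protocol 5.5). Only potency, duration and repeat use of topical agents are unstated.
- *Rescue is not tabulated at all.* The agents do appear under SAP 7.3. What is missing is any means of recognising them as rescue.
- *A rescued subject is a responder at every later visit.* OC carries nothing forward; each visit is scored on its own value.
- *Pre-rescue assessments are wasted.* If rescue is given at a scheduled visit, the pre-rescue assessment is available to that visit's summary. For unscheduled visits the SAP states no rule either way.
- *SAP 8.0 decides to ignore rescue.* It covers primary and key secondary endpoints only and is silent on the exploratory ones.
- *The effect is largest in all five dupilumab non-responder endpoints.* No rescue rates are given. Subjects who missed EASI 100 include some who reached EASI 90, and they are not an obvious high-rescue group.

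**Conclusion.** The point holds as a limit on interpretation. Under the current text the efficacy percentages describe upadacitinib with or without topical rescue, and no planned output shows how much rescue contributed. This follows from the wording of Protocol 5.3, 5.4 and 7.3 and SAP 5.0, 7.3, 9.1 and 9.2, and needs no numerical assumption.

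The size does rest on assumptions. The gap is r × q: negligible if rescue is rare (at most 1.6 points at r = 2% with q up to 80%) and material if it is moderately common (2.5 to 8 points at r = 5–10% and q = 50–80%). A reader might take r × q as the amount by which upadacitinib efficacy is overstated. It is not that. It is the distance between two estimands, and some response after rescue may be due to upadacitinib. The primary safety endpoints do not depend on this choice.

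**What to change.** Analysis and reporting only; no rescue rule changes.

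1. **SAP 9.2:** keep OC as the main analysis and state that it includes values after topical rescue regardless of rescue (treatment policy for topical rescue).
2. **SAP 5.0 or 7.3:** tabulate the number and percentage of subjects with topical rescue and with systemic rescue, by visit interval and M16-046 group. Define topical rescue by agent class, reason for use and start date, because Protocol 5.3 and 5.4 allow some topical products outside rescue.
3. **SAP 9.5:** add one supportive analysis of the binary endpoints, at least the five dupilumab non-responder endpoints. Count a subject as a non-responder from the start of topical rescue in M19-850, and label the result a conservative bound.
4. **Continuous endpoints:** do not exclude post-rescue values. That would drop subjects who flared and could make the mean improvement look better. If a supportive summary is wanted, use the last pre-rescue value.

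Cost: SAP wording and a few extra tables. Protocol 5.4 already collects the dates and reason for use of every medication, so no new data are needed. The drawback is that the supportive rates will be lower wherever rescued subjects respond, and harsh on a subject who had one short course and then did well without it. For that reason they should sit beside the OC table and not replace it.
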